9.4.2 ANALYSIS OF THE PRIMARY ENDPOINT(S)

Our sample encompasses persons with cognitive impairment, some of whom may be unable to respond to study assessments. Therefore, primary outcomes at 6 months are assessed from the perspective of the family caregiver, although all measures are fielded in parallel to patient and analyses will be conducted in parallel to examine both perspectives. Baseline enrollment visits and assessments are conducted after obtaining informed oral consent. Follow-up assessments are conducted by telephone by study staff to afford greater flexibility and privacy. Caregivers are offered the opportunity to complete web-based follow-up assessments. Composite outcomes will be operationalized as previously described in source analyses of the psychometric properties of each battery. The outcomes that we assess have been identified as defining success in advance care planning and for which strong measures now exist.^{135,136} We examine two primary outcomes, as follows:

Quality of Communication. We assess family caregiver-reported quality of communication at 6 months, using the end-of-life subscale (n=7 items) of the validated instrument.^{137,138} The QOC has excellent internal consistency and strong evidence of reliability and validity: we focus on the end of life subscale which is most pertinent to advance care planning in the target population. We follow the question wording stipulated by Engelberg (2006), with two modifications. First, we have revised the question stem to reflect the perspective of the family. Second, we have revised the question stem to reflect our interest in communication with the primary care team as opposed to “their doctor”.

Satisfaction with Care at the End-of-Life in Dementia (SWC-EOLD) is a 10-item instrument measured on a 4-point Likert scale that ranges from 1 “strongly disagree” to 4 “strongly agree” with a summary score ranging from 10-40 in which higher values indicate higher satisfaction.^{90,139,140} We field this instruments as originally described by Volicer to bereaved family caregivers of patient participants who die by 24 months.

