1 PROTOCOL SUMMARY

1.1 SYNOPSIS

| | |
|---|--|
| Title: | SHARE: Sharing Healthcare Wishes in Primary Care |
| Grant Number: | R01AG058671 |
| Study Description: | This study will test a multicomponent communication intervention, referred to as SHARE, to proactively engage family members or friends (interchangeably referred to as “family” and/or “caregiver”) and support advance care planning in primary care. We will conduct a two-group randomized trial at up to 10 primary care practices in which 124 dyads (+/- 10) will receive a control protocol of minimally enhanced usual care and 124 dyads (+/- 10) will receive the SHARE protocol. We test the efficacy of SHARE on quality of communication (primary outcome) and advance care planning processes (secondary outcomes) at 6 months among primary care patients with cognitive impairment (mild-severe) and family caregiver dyads. For patients who die by 24 months, we examine the quality of end of life care and bereaved family caregiver experiences with medical decision-making (secondary outcomes). |
| Objectives: | To test the efficacy of SHARE on improved quality of communication (primary outcome) and end-of-life experiences (secondary outcomes) of primary care patients with cognitive impairment (mild-severe) and family caregivers. |
| Endpoints: | Primary Endpoint: Quality of Communication and Quality of End of Life Care Secondary Endpoints: Advance care planning processes and bereaved family caregiver experiences with medical decision-making |
| Study Population: | We plan to enroll a sample of 248 (+/- 20) person-family dyads comprising primary care patients with cognitive impairment ages 80 years or older and the person who helps them the most with medical decision making, who we refer to as their caregiver. This study focuses on persons ages 80 and older with cognitive impairment (mild-severe) . |
| Stage: | Stage 1 Behavioral Intervention |
| Description of Sites: | We will conduct the trial at up to 10 primary care practices within two health systems (Johns Hopkins Community Physicians, and MedStar Health System) in the Baltimore/Washington area. |

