2 INTRODUCTION

2.1 STUDY RATIONALE

Advance care planning is a process that supports adults at any age or stage of health in understanding and sharing their personal values, life goals, and preferences regarding future medical care.¹ Early initiation of advance care planning is an imperative in ADRD care due to the long course of illness and its progressive and devastating effects on decision-making capacity. However, little attention has been directed at developing strategies to improve advance care planning for persons with ADRD and their family caregivers in primary care, which is the most common setting of initial diagnosis^{2,3} and ongoing medical management.^{4,5}

This study proposes to systematically develop and test a communication intervention, referred to as SHARE, to proactively engage family caregivers and normalize advance care planning in primary care. Our goal is to engage family caregivers in longitudinal interactions with primary care clinicians and stimulate and support advance care planning discussions in primary care. We focus on persons with mild, moderate, and severe cognitive impairment regardless of clinical diagnosis because of the importance of addressing

advance care planning early in the disease trajectory,^{6,7} the under-diagnosis of ADRD⁸⁻¹⁰ and because of the greater implementation potential of a protocol with broader applicability. We hypothesize that as compared with the minimally enhanced control care group, caregivers in the intervention group will report better quality of communication about end of life care with primary care clinicians at 6 months (primary outcome). We further examine the effects of the intervention on advance care planning processes (secondary outcomes) at 6 months. For patients who die by 24 months, we examine the quality of end of life care and bereaved family caregiver experiences with medical decision-making (secondary outcomes).

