3.2 SECONDARY OBJECTIVES

We further test the efficacy of SHARE on advance care planning processes at 6 months. We hypothesize that intervention caregivers will be more highly engaged in advance care planning than control caregivers as measured by caregiver-reported readiness to engage in advance care planning and having documented advance directive in the patient's electronic health record at 6 months. We expect patient-reported outcomes will mirror those reported by caregivers and that outcomes will be achieved without adversely affecting the therapeutic alliance with the primary care clinician or perceptions of shared decision-making with the primary care team.

For patients who die by 24 months, we examine the quality of end of life care and bereaved family caregiver experiences. Among patients who die between enrollment and 24 months, we hypothesize caregivers in the intervention group will report higher quality of end-of-life care than those in the control group as measured by the Satisfaction with Care at the End-of-Life in Dementia scale. We expect that that bereavement outcomes will be superior among intervention caregivers than control group caregivers as measured by less decisional conflict, less decisional regret, and fewer symptoms of anxiety and depression. Finally, we expect that decedents in the intervention group will be less likely to experience burdensome care at the end of life than decedents in the control group.

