4 STUDY DESIGN

4.1 OVERALL DESIGN

This is a two-group single-blind randomized Phase 2 efficacy trial that will be conducted at up to 9 primary care practices in which 124 (+/- 10) dyads will receive a control protocol of minimally enhanced usual care and 124(+/- 10) dyads will receive usual care augmented with the SHARE protocol. We test the efficacy of multicomponent communication intervention, referred to as SHARE, on quality of communication (primary outcome) and advance care planning processes (secondary outcomes) at 6-, 12-, and 24-months

among primary care patients with cognitive impairment (mild-severe) and family caregiver dyads. For patients who die by 24 months, we examine the quality of end of life care (primary outcome) and bereaved family caregiver experiences with medical decision-making (secondary outcomes). Following enrollment and follow-up procedures, a small number of intervention group dyads will be selected to participate in a focus group interview to assess opinions and impressions of the SHARE experience. Primary care patients and family caregiver dyads will consent to being contacted for potential focus group participation.

SHARE encompasses usual care, supplemented with the following four therapeutic elements: 1) a letter from the practice introducing the initiative, 2) access to a designated staff member (e.g., medical assistant, social worker or nurse, community health worker, or lay facilitator) trained to lead advance care planning discussions, 3) person-family agenda-setting to align perspectives about the role of the caregiver and stimulate discussion about goals of care, and 4) education about communication and available resources, including a 44-page brochure developed by the National Institute on Aging entitled “A Guide for Older People: Talking with your Doctor”, a blank easy to complete advance directive, and facilitated registration to the patient portal (for patient and caregiver) to extend electronic interactions and information access to family. The control group will receive minimally enhanced usual care with print educational materials that include the 44-page brochure developed by the National Institute on Aging entitled “A Guide for Older People: Talking with your Doctor” and a blank easy to complete advance directive.

[figure not shown]

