9 STATISTICAL CONSIDERATIONS

9.1 STATISTICAL HYPOTHESES

Objectives and hypotheses related to primary outcomes are as follows:

We test the efficacy of SHARE on quality of communication (primary outcome) and advance care planning processes (secondary outcomes) at 6 months among primary care patients with cognitive impairment (mild-severe) and family caregiver dyads. We hypothesize that as compared with the control group, caregivers in the intervention group will report better quality of communication about end of life care with primary care clinicians at 6 months (primary outcome).

Objectives and hypotheses related to secondary outcomes are as follows:

We further test the efficacy of SHARE on advance care planning processes at 6 months. We hypothesize that intervention caregivers will be more highly engaged in advance care planning than control caregivers as measured by caregiver-reported readiness to engage in advance care planning and having documented advance directive in the patient's electronic health record at 6 months. We expect patient-reported outcomes will mirror those reported by caregivers and that outcomes will be achieved without adversely affecting the therapeutic alliance with the primary care clinician or perceptions of shared decision-making with the primary care team.

For patients who die by 24 months, we examine quality of end of life care and bereaved family caregiver experiences with medical decision-making. We hypothesize caregivers in the intervention group will report higher quality of end-of-life care than those in the control group as measured by the Satisfaction with Care at the End-of-Life in Dementia scale. We expect that bereavement outcomes will be superior among intervention caregivers than control group caregivers as measured by less decisional conflict, less decisional regret, and fewer symptoms of anxiety and depression. Finally, we expect that decedents in the intervention group will be less likely to experience burdensome care at the end of life than decedents in the control group.

We expect patient-reported outcomes will mirror those reported by caregivers and that outcomes will be achieved without adversely affecting the therapeutic alliance with the primary care clinician.

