9.3 POPULATIONS FOR ANALYSES

The populations for analyses encompass a sample of about 248 person-family dyads who meet eligibility criteria specified in Section 5 of this protocol. The table below summarizes information that will be assessed from patient and family participants.

| 9.3 Table of Assessments | | | | | | | | | | | | |
|---|---|---------------------------------|-------|--------------------------------|------------|-------------|----|----|-----|-----|-----|--|
| Construct | Measure | Items | Range | Validity | Source | Outcome | BL | 6M | 12M | 24M | EOL | |
| Outcomes @ 6 Months, Patient and Family Experience | | | | | | | | | | | | |
| QOC (Primary) | Quality of EOL Communication ^{51,84-87} ; General QOC Subscale and Global (Secondary) | 7 7 | 0-70 | $\alpha=0.79$ $\alpha=0.91$ | P, F | F@6M | X | X | X | X | | |
| ACP (Secondary) | Sudore 4-item ACP engagement μ ^{88,89} | 4 | 0-20 | $\alpha=0.84$ | P, F | F@6M | X | X | X | X | | |
| | Advance Directive Completion ²⁰ | -- | Y/N | -- | EMR | E@6m | | X | X | X | X | |
| Outcomes @ EOL, Quality of Care and Surrogate Decision-Making Experience | | | | | | | | | | | | |
| Quality of EOL (Primary) | Satisfaction w/ Care at the EOL in Dementia ^{51,90} | 10 | 10-40 | $\alpha=0.90$ | F | F@EOL | | | | | X | |
| Surrogate Decision- Making (Secondary) | Decisional conflict scale ⁹¹⁻⁹³ | 16 | 0-100 | $\alpha=0.78$ | F | F@EOL | | | | | X | |
| | Decisional regret – Brehaut ⁹⁴⁻⁹⁶ | 5 | 0-100 | $\alpha=0.81-0.92$ | F | F@EOL | | | | | X | |
| | Anxiety: GAD-7 ^{97,98} | 7 | 0-21 | $\alpha=>0.92$ | F | F@EOL | X | X | X | X | X | |
| EOL care (Secondary) | Burdensome care | | | | EMR/F | EMR@ EOL | | | | | X | |
| Primary Care Interactions and Communication | | | | | | | | | | | | |
| Therapeutic alliance | Human Connection Scale ⁹⁹⁻¹⁰³ | 16 | 16-64 | $\alpha=0.90$ original | F | - | X | X | X | X | | |
| Shared Decision- Making | CollaboRATE μ ¹⁰⁴⁻¹⁰⁷ | 3 | 0-100 | $\alpha=0.89$; 0-9/item | P, F | - | X | X | X | X | | |
| Primary Care Interactions | Frequency/Mode of Contacts ^{29,108,109} (IH) | 5 | -- | Homegrown | F, E | - | X | X | X | X | X | |
| | Use of patient portal | -- | -- | -- | EMR | - | X | X | X | X | X | |
| Implementation, Fidelity/Implementation Processes, Clinic Context (Note: these items will be limited to intervention participants) | | | | | | | | | | | | |
| Acceptability | Acceptability: Recruitment & retention | Consort diagram | | | | - | | | | X | | |

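### Quality of end-of-life care is primary in four places and secondary in six; of the two outcomes called primary, only 6-month quality of communication has an alpha, a power and a specific model

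*Combined protocol and SAP*

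**What the plan says.** Four places give quality of end-of-life care primary status:

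- 1.1 Synopsis, Endpoints row: "Primary Endpoint: Quality of Communication and Quality of End of Life Care".
- 4.1, for patients who die by 24 months: "we examine the quality of end of life care (primary outcome").
- 9.3 table, SWC-EOLD row: "Quality of EOL (Primary").
- 9.4.2: "We examine two primary outcomes, as follows", followed by QOC and SWC-EOLD.

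Section 9.4.3 fits this version: its four bereavement secondaries are decisional conflict, decisional regret, anxiety and burdensome care, without SWC-EOLD.

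Six places treat it as secondary:

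- 1.1 Synopsis, Study Description row, and 2.1, in the same words: "we examine the quality of end of life care and bereaved family caregiver experiences with medical decision-making (secondary outcomes").
- 1.1 Synopsis, Objectives row, in broader terms: "To test the efficacy of SHARE on improved quality of communication (primary outcome) and end-of-life experiences (secondary outcomes").
- 3.2, under Secondary Objectives: "Among patients who die between enrollment and 24 months, we hypothesize caregivers in the intervention group will report higher quality of end-of-life care", measured by SWC-EOLD.
- 9.1, where the SWC-EOLD hypothesis follows the line "Objectives and hypotheses related to secondary outcomes are as follows".
- 9.2, where satisfaction with end-of-life care falls in the text on secondary outcomes.

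Section 3.1 states the primary objective for 6-month QOC alone, and 9.4.1 refers to the primary outcome in the singular.

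**The concern.** The primary endpoint set decides what counts as a successful trial, and this plan supports two incompatible sets. The disagreement runs through the statistical section itself: 9.3, 9.4.2 and 9.4.3 agree with one another on two primaries, while 9.1, 9.2 and 9.4.1 agree with one another on one. A success claim on SWC-EOLD alone could cite the Endpoints row and 9.4.2, although it would contradict 9.1, 9.2 and 9.4.1. A claim on QOC alone would fit 9.1, 9.2 and 9.4.1 but leave an outcome labelled primary unaddressed. Once results are known, either choice could be defended from the protocol text.

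**Working it through.** **What is specified for each outcome called primary**

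| Item | QOC at 6 months | SWC-EOLD |
|---|---|---|
| Alpha | two-sided 0.05 (9.2) | none stated |
| Power and effect | above 80% for 0.39 SD, 222 dyads (9.2) | none; 92 responses called enough for monitoring effects (9.2) |
| Model | hierarchical ANCOVA on baseline QOC, Proc MIXED (9.4.1) | none assigned |
| Rule if both are primary | none | none |

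The QOC model cannot carry over as written. The 9.3 table collects SWC-EOLD only at end of life, so it has no baseline score. The GLIMMIX model in 9.4.1 is for dichotomous outcomes. Section 9.2 does give a power for burdensome care, which is a listed secondary.

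**Inputs** (9.2 unless noted): unadjusted effect 0.30 SD; baseline to 6-month correlation 0.65; 248 enrolled, 10% attrition, 222 retained; 50% mortality, so 124 deaths; 25% attrition, 92 responses; allocation 1:1 (5.5.3). Power below is for a two-sided two-sample t-test (noncentral t) unless marked otherwise.

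**Reproducing 9.2**

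- Adjusted effect: 0.30/√(1 − 0.65²) = 0.395; the plan uses 0.39.
- Retained: 248 × 0.90 = 223; the plan uses 222.
- QOC power, 111 per arm, 0.39 SD, alpha 0.05: **82.5%**, which agrees with the plan.
- Burdensome care, 62 per arm, 30% vs 10%, pooled z-test: 80.3%, which agrees.
- Bereaved responses: 124 × 0.75 = 93; the plan uses 92.

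**Either outcome at 0.05 counts as success (not stated in the plan)**

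- Independent tests: 1 − 0.95² = **9.75%**.
- If all 92 bereaved responders also gave a 6-month QOC score, the correlation of the two test statistics is the outcome correlation × √(92/222) = outcome correlation × 0.644. Bivariate normal results:

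| Assumed outcome correlation | Correlation of statistics | Familywise error |
|---|---|---|
| 0 | 0 | 9.75% |
| 0.5 | 0.32 | 9.48% |
| 0.8 | 0.52 | 9.03% |
| 1.0 | 0.644 | 8.59% |

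Deaths before 6 months reduce the overlap and move these figures towards 9.75%.

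**Alpha split to 0.025 each**: QOC power with 111 per arm and 0.39 SD falls to **74.1%**, below the stated 80%.

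**Both must succeed**: familywise error does not exceed 5%, but joint power cannot exceed the lower of the two powers.

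**SWC-EOLD with 92 responses (46 per arm)**

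- Difference detectable with 80% power: **0.59 SD** at 0.05 and 0.65 SD at 0.025. The normal approximation at 0.05 gives (1.960 + 0.842) × √(2/46) = 0.584. With 93 responses the t-test figure is 0.587.
- The plan assumes no effect for SWC-EOLD, so a range is shown (normal approximation). The 0.39 SD is not used, because it comes from adjustment for a baseline score that SWC-EOLD lacks.

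| Assumed effect | Power at 0.05 | Power at 0.025 |
|---|---|---|
| 0.30 SD | 30% | 21% |
| 0.50 SD | 67% | 56% |
| 0.60 SD | 82% | 74% |

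**The case against.** The strongest reply is that the passages driving inference (3.1, 9.1, 9.2 and 9.4.1) all point to QOC alone, so only a few labels need correcting. It is true that the design is coherent on that reading and that error control is not already lost. But 9.4.2, the section that defines the primary analysis, says otherwise and 9.4.3 follows it, so a reader cannot tell which version governs.

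A second reply is that primary may mean the lead outcome within a domain. The 9.3 table has separate 6-month and end-of-life blocks, each with its own primary row, and 4.1 ranks outcomes among patients who die. That softens those two labels but does not explain 9.4.2 or the Endpoints row.

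Third, the count of six is partly by placement. In 3.2, 9.1 and 9.2 the status comes from a heading or lead-in, the Objectives row uses broader wording, and the closing tag in the synopsis description and 2.1 could be read as covering only its second item. This is fair as to how explicit the six are. The placements in 3.2 and 9.1 are enough for the contradiction.

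Fourth, 9.2 presents the bereavement data partly as a source of effect sizes for later trials, so the absence of an SWC-EOLD power is a gap only if the outcome is primary. Decisional conflict and regret, also collected only at end of life, share the missing model. Both points are correct, and both favour treating SWC-EOLD as secondary.

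**Conclusion.** The concern holds, and the matter must be fixed. The plan states two incompatible primary endpoint sets and supports only one of them with an alpha, a power and a model. With QOC alone as primary, error is 5% and power about 82%. The 8.6% to 9.75% familywise error is conditional: it applies only if success on either outcome at 0.05 were accepted, and it assumes non-negative correlation between the outcomes. The 74% QOC power applies only if alpha were split equally. The 0.59 SD detectable difference assumes 92 responses divided equally between the arms and no covariate adjustment.

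**What to change.** - In 1.1, 4.1, 9.3 and 9.4.2, name the caregiver-reported QOC end-of-life subscale at 6 months as the single primary endpoint.
- Add SWC-EOLD to the bereavement secondaries in 9.4.3, in line with 3.2, 9.1 and 9.2.
- In 9.4.1, write a model for SWC-EOLD without a baseline score, for example the existing mixed model with dyads within clinics and treatment group as the main term. The same sentence can cover decisional conflict and regret.
- If a confirmatory claim on SWC-EOLD is wanted, state that it is tested at two-sided 0.05 only after QOC is significant at 0.05. This keeps familywise error at 5% and QOC power unchanged. Section 9.2 should then give the 0.59 SD detectable difference.

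The cost is wording in six sections (1.1, 4.1, 9.3, 9.4.1, 9.4.2, 9.4.3), plus 9.2 if the detectable difference is added. No patients or data are added. The change should be made before outcome data are unblinded; the documents do not state the trial's current status.

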9.4.3 ANALYSIS OF THE SECONDARY ENDPOINT(S)

Two categories of secondary outcomes will be assessed: measures of patient and family experiences at six-months, and bereaved family caregiver experiences, for patients who die. Each are described in turn:

Patient and Family Experiences encompasses 3 metrics relating to advance care planning as follows.

1. **Readiness to engage in advance care planning.** The Advance Care Planning Engagement Survey is a validated patient-reported questionnaire that assesses advance care planning process measures (knowledge, contemplation, self-efficacy, and readiness) on a 5-point Likert scale, and action measures (discussing and documenting advance care planning) using dichotomous (yes/no) response categories.^{141,142} The Survey has high internal consistency, test-retest reliability, and discriminant validity, and is responsive to change¹⁴¹⁻¹⁴³ but persons with cognitive impairment were excluded from its development and testing. In keeping with the developmental nature of the Aim 2 pilot⁶⁰ we will examine the feasibility and psychometric properties of the an abbreviated version of the survey in the target population. The original 82-item instrument took 49 minutes to administer, on average¹⁴¹ and although we planned to field the abbreviated 15-item advance care planning engagement survey,⁸⁸ early work in a similar population suggested that respondents had a difficult

time differentiating between questions, and the battery was perceived by research staff as being unnecessarily long. In this study we therefore field the 4-item engagement instrument and draw on VanScoy's work (2019) which identifies a parallel survey for surrogate decision-makers involving 3 factors that pertain to shared decision-making (7 items), contemplation (4 items), and readiness (6 items). ⁸⁹ Following the principal of fielding parallel questions to patients and families, we examined the Van Scoy 6-item readiness domain for potential inclusion on the family questionnaire and selected 4 items that most closely paralleled the patient version (items 12-14, and 16 from Van Scoy). We modify question stems for several items to replace "loved one" with "your RELATIONSHIP" so the items are neutral with respect to relational quality.

2. **Documentation of advance directive completion in the electronic health record** is defined as having a durable power of attorney or a living will documented in the primary care electronic health record.^{51,144,145} We do not consider the Medical Order for Life Sustaining Treatment (MOLST) in inclusion/exclusion criteria for the study or as an outcome of advance directive completion as the completion of a Maryland MOLST is mandatory in certain situations (e.g., on transfer between settings of care) and is not indicative of having had an advance care planning discussion or naming a durable power of attorney; the Maryland MOLST does not conform to the National POLST Paradigm.^{146,147}

Bereaved Family Caregiver Experiences. Among patients who die by 24 months, we assess 4 secondary outcomes relating to bereaved caregiver experiences with medical decision-making and burdensome care among older adults as follows.

1. **Decisional conflict.** The Decisional Conflict Scale is a 16-item instrument scored on a 5-point Likert scale ranging from 1 to 5.⁹¹ Aggregate scores range from 0 (no conflict) to 100 (extremely high conflict).⁹¹⁻⁹³
2. **Decisional regret** will be assessed using a 5-item instrument that assesses the extent to which decision-makers experience regret about care. Response options are assessed using a 5-item Likert scale in which scores of 1 indicate the least regret and 5 the most regret. Scores are then reduced by 1 point and multiplied by 25 for a scale that ranges in value from 0 to 100. Prior studies have categorized scores of 0 as no regret, 1 to 25 as mild regret, and more than 25 as heightened regret.⁹⁴⁻⁹⁶
3. **Symptoms of anxiety.** The Generalized Anxiety Disorder 7-item (GAD-7)⁹⁷ is a validated instrument that ask about symptoms of anxiety using a two-week recall period with response categories that vary from 0 ("not at all") to 3 ("nearly every day"). Item responses are summed to construct composite scores.
4. **Burdensome care.** Burdensome care will be measured by any intensive care unit use or life prolonging care (cardiopulmonary resuscitation, mechanical ventilation, tracheostomy, dialysis, artificial nutrition, chemotherapy) within 30 days of death^{101,102} using dates and services abstracted from medical records and the Chesapeake Regional Information System (CRISP), Maryland's Health Information Exchange, which includes all hospital encounters.

